Intention-to-treat (ITT) All randomized study subjects. This will be seen as the primary population for the analysis. Per Protocol (PP) All randomized study subjects completing the whole study period (complete cases). For a specific analysis, study subjects with missing data on any of the variables in the model will be excluded from the analysis. Analyses of this population is seen as a sensitivity analysis to investigate whether conclusions are sensitive to assumptions regarding the pattern of missing data.

Covariates and Subgroups

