To allow for 15-20% loss to follow-up (our previous trials have each achieved retention rates of >90%), we estimate a sample of 600 AMSM to be enrolled across the four regions. Participants may continue the study even if they miss surveys intermittently over the data collection period. We will compare those who completed different follow-up interviews with those who did not on key predictors from the baseline assessment to check for possible sampling bias due to missing data. Missing data will be minimized by the web-based entry for all measures. We will handle missing data by applying likelihood-based methods that include partial information in cases that drop out prematurely and develop nonresponse adjustment and post-stratification weights to account for survey non-participation. The use of Expectation-Maximization (EM) algorithm and multiple imputation approach

in longitudinal analyses will help overcome missing data concerns when appropriate. When the missing at random assumption appears suspect, we will not replace missing data to avoid bias.

Summary of Study Data

All continuous variables will be summarized using the following descriptive statistics: n (non-missing sample size), mean, standard deviation, median, maximum, and minimum. The frequency and percentages (based on the non-missing sample size) of observed levels will be reported for all categorical measures. In general, all data will be listed, sorted by site, treatment, and subject, and when appropriate by visit number within subject. All summary tables will be structured with a column for each treatment in the order (Control, Experimental) and will be annotated with the total population size relevant to that table/treatment, including any missing observations.

Efficacy Analyses

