Analysis tests the efficacy of the iREACH intervention as compared to a delayed intervention condition, to create positive changes in the following outcomes: *primary outcomes*: changes in confidence to engage in HIV prevention behaviors and changes in HIV knowledge and *secondary outcomes*: changes in sexual behavior and change in HIV testing behavior over the 12-month follow-up period. Descriptive statistics of the behavioral, psychosocial, and demographic characteristics of the participants will be described for all and by group (intervention and control). These will be compared between treatment groups using t-tests or Wilcoxon rank sum tests for continuous variables and chi-square tests for categorical variables. In addition, we will use the general framework of generalized linear mixed models (GLMM) to test for intervention effects over time. Note that some of our outcomes are binary, some count and some continuous traits and thus need to be treated differently. The general form of the GLMM will be $(\mu_{ij}) = \beta_{0i} + \beta_{\text{cov Covariates}_{ij}} + \beta_{\text{Time}_{j}} + \beta_{\text{Intervention Group}_i} + \beta_{\text{Group} \times \text{Time}_i}$, where μ_{ij} is the mean response corresponding to subject i at Time j (baseline and 4 follow-ups) with the appropriate link function (identity for continuous outcome, logit for binary outcome and natural log for count outcomes); Group =1 if the i -th subject is in the intervention group and 0 if the i -th subject is in the attention-control group. The interaction coefficients $\beta_{\text{Group} \times \text{Time}}$ are of interest here, measuring the difference in the rate of change in outcomes across the two treatment groups over time in the primary and secondary outcomes. Models will be compared according to information criterion like AIC, BIC. For some binary outcomes like HIV testing, we will perform an aggregate analysis after collapsing across the repeated measures using simple logistic regression comparing whether the probability of having tested at least once over the entire FU period is different across treatment groups, after adjusting for baseline values. To ensure robustness, we will also apply an exchangeable working correlation structure to its corresponding generalized estimating equation (GEE) model.

Reporting Conventions

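### Declining to impute when missing at random is in doubt does not avoid bias, and no planned analysis examines missing-not-at-random dropout

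*SAP*

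**What the plan says.** The SAP's Missing Data section plans for 15-20% loss, and notes that "our previous trials have each achieved retention rates of >90" per cent. It will use "likelihood-based methods that include partial information in cases that drop out prematurely" and will "develop nonresponse adjustment and post-stratification weights to account for survey non-participation". EM and multiple imputation are to be used where appropriate. Then comes the rule at issue: "When the missing at random assumption appears suspect, we will not replace missing data to avoid bias". No alternative analysis is named for that case.

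The only diagnostic named in that section is: "We will compare those who completed different follow-up interviews with those who did not on key predictors from the baseline assessment".

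Two other analyses bear on the point. Under Analysis Populations, the Per Protocol set consists of completers, and the SAP says of it: "Analyses of this population is seen as a sensitivity analysis to investigate whether conclusions are sensitive to assumptions regarding the pattern of missing data". Under Efficacy Analyses: "To ensure robustness, we will also apply an exchangeable working correlation structure to its corresponding generalized estimating equation (GEE) model". The protocol's Statistical Analysis section specifies maximum likelihood for the mixed model and also a GEE, and says nothing about missing data. Neither document names a delta-adjusted, tipping-point, pattern-mixture, selection-model or reference-based analysis.

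**The concern.** Leaving values unimputed does not take the missing-data assumption out of the analysis. A likelihood mixed model fitted to the available records fills the gap implicitly through the observed visits, and that is valid under MAR. Nonresponse and post-stratification weights use observed variables only, so they need an assumption of the same kind. When MAR is doubted, the plan therefore drops one MAR-based method and reports others.

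The trigger has no decision rule, and the one check cannot supply it. A baseline difference between completers and non-completers is compatible with MAR, and the absence of a difference does not exclude MNAR.

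What is at stake is bias in the primary contrast. The arms differ in ways that could affect who keeps answering surveys: one has the full app with peer mentors, the other a resource locator with delayed access. If dropout depends on unseen outcomes differently by arm, the reader cannot see how different the dropouts would have to be to change the conclusion.

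**Working it through.** **The plan's own figure.** 600 enrolled and 500 retained implies a loss of 1 - 500/600 = 16.7%, inside the stated 15-20%. Retained numbers at 15% and 20% loss are 510 and 480. The enrolment figure reproduces.

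**General rule.** With the same share missing in both arms, bias in the arm difference = missing share × between-arm departure from MAR. For a 0.5 SD departure in one arm: 0.15 × 0.5 = 0.075, 0.20 × 0.5 = 0.10 and 0.10 × 0.5 = 0.05 SD.

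**Worked scenario A (assumed).** The true effect is zero. In the intervention arm, month-12 dropout depends on the unseen month-12 score; in control it is random.

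Inputs from the documents:
- 300 per arm (SAP, Randomization and Blinding).
- Within-person correlation r = 0.25 and 0.75 (SAP, Sample Size).
- Primary outcomes at baseline, month 6 and month 12 (SAP, Study Assessments table; the model under Efficacy Analyses is written for four follow-ups, but the table is used here).
- 15-20% loss, plus 10% from the cited earlier retention.

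Assumed: r = 0.5 as a midpoint, unit variance, exchangeable correlation, time as categories, everyone seen at month 6, and dropout logit = a - 0.65 × y12 with a = -1.505, -1.875 and -2.36 for 20%, 15% and 10% loss.

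1. Exact integration gives completer means m = 0.1218, 0.0924, 0.0624 SD and variances v = 0.943, 0.953, 0.966 at 20%, 15%, 10% loss.
2. Regressing y12 on the two earlier visits among completers gives each a coefficient b = rv / (2r²v + 1 + r - 2r²). The MAR likelihood bias is m(1 - 2br). At 20% and r = 0.25: b = 0.2358/1.2429 = 0.190, and the bias is 0.1218 × 0.905 = 0.110.
3. The residual variance is s² = 1 - 2r²/(1 + r). With loss share d, SE² = 2 × [(2(1 - r) - s²)/300 + s²/(300(1 - d))]. At 20% and r = 0.25: 2 × [0.6/300 + 0.9/240] = 0.0115, so SE = 0.107. The effect detectable at 80% power is 2.80 × SE.

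Each cell below is for r = 0.25 / 0.5 / 0.75. False-positive rates come from 8,000 simulated trials (generalised least squares, r known).

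| Loss | Bias (SD) | Detectable effect (SD) | Bias / detectable | False-positive rate |
|---|---|---|---|---|
| 20% | 0.110 / 0.083 / 0.045 | 0.300 / 0.247 / 0.176 | 37 / 34 / 26% | 17.8 / 15.0 / 11.0% |
| 15% | 0.084 / 0.063 / 0.034 | 0.295 / 0.242 / 0.172 | 28 / 26 / 20% | 12.5 / 10.9 / 8.2% |
| 10% | 0.056 / 0.042 / 0.023 | 0.289 / 0.237 / 0.168 | 19 / 18 / 14% | 8.7 / 7.6 / 6.8% |

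Modelling time as linear lowers the bias by 0.002-0.006 SD.

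**Scenario B (assumed).** As A, but control dropout depends on the outcome half as strongly (slope 0.325). At 20% loss the bias is 0.053 / 0.040 / 0.022 SD, about 13-18% of the detectable effect. The false-positive rate is 7.8 / 7.4 / 6.4% by normal approximation.

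**Dropout alike in both arms.** The two biases cancel; simulated false-positive rates were 4.5-5.3%.

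**Would the planned checks reveal it?** All for scenario A at 20% loss.
- GEE against likelihood: the difference is below 0.001 SD (1,000,000 simulated records per arm).
- Complete-case change from baseline: bias m(1 - r) = 0.091 / 0.061 / 0.030 SD. It differs from the likelihood result by 0.019 / 0.022 / 0.015 SD and lies in the same direction.
- Baseline comparison: the month-12 gap between completers and dropouts is 0.1218/0.20 = 0.609 SD, so the baseline gap is r × 0.609 = 0.15 / 0.30 / 0.46 SD. Within one arm (240 against 60), SE = √(1/240 + 1/60) = 0.144, and power is about 18 / 56 / 89%. The check is weakest where the bias is largest.

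**Tipping point.** The shift in one arm that brings an effect of detectable size to zero is detectable effect / missing share, computed before rounding: 1.50 / 1.24 / 0.88 SD at 20%, 1.96 / 1.61 / 1.14 SD at 15%, and 2.89 / 2.37 / 1.68 SD at 10%. If the SE is unchanged, significance goes earlier, at (2.80 - 1.96)/2.80 = 30% of these shifts.

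**The case against.** The strongest reply is that the sentence follows directly on EM and multiple imputation, so it may mean only that MAR-based imputation will not be used when MAR is doubted. That is a sensible restraint, but the estimates still reported in that case depend on MAR, and nothing is named to replace the imputation.

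The SAP also labels the complete-case analysis a check on assumptions about the pattern of missing data. That should be credited: missing data are not ignored. But the check compares two sets of assumptions, neither of which lets dropouts differ on unseen outcomes.

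The criticism that the magnitudes are scenarios stands. Scenario A is one-sided and fairly strong. The milder scenario B and the 10% case give much smaller figures, and like dropout in both arms gives almost none. The figures also apply to continuous outcomes only.

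The calculation assumes everyone is seen at month 6, whereas the SAP expects premature dropout and missed surveys. This assumption is conservative: if the dropouts are lost before month 6, the bias at 20% loss rises from 0.110 to 0.115 SD at r = 0.25 and from 0.045 to 0.055 SD at r = 0.75.

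**Conclusion.** The concern holds. The rule's stated purpose cannot be met by the analyses that remain, its trigger is undefined, and neither document contains an MNAR analysis. That much follows from the text and needs no assumed mechanism.

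The consequence for this trial is unknown. Under the assumed one-arm mechanism with 15-20% loss, the bias would be 0.034-0.110 SD, or 20-37% of what the same contrast can detect. The false-positive rate would be 8-18% instead of 5%. Under scenario B at 20% loss it would be 6-8%. The primary model can stand; what is missing is a way to judge how far its result depends on MAR. This should be changed before analysis, but it does not invalidate the design.

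A minor related point: the Per Protocol set requires completion of the full study period. Under the protocol's Study Design that could mean 15 months for control and 12 for intervention, while the efficacy period in the SAP is 12 months.

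**What to change.** - Delete the sentence. Keep the likelihood analysis of all randomised participants as primary, stated as valid under MAR.
- Prespecify a delta-adjusted (pattern-mixture) multiple imputation at month 12. Shift imputed values in the unfavourable direction, separately by arm, over a range wide enough to reach the tipping point: about 0 to 1.5 SD at 20% missing, to about 2 SD at 15%, and to about 2.9 SD if loss is only 10%. Report the shifts at which significance and then the effect itself are lost.
- Say how shifts are handled when they would pass the end of a bounded scale. For binary outcomes such as HIV testing, define the shift on the log-odds scale.
- Keep the complete-case and GEE analyses if wanted, but do not present them as tests of MNAR. Report the baseline comparison as descriptive.
- Define completers by the month-12 survey in both arms.

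The cost is SAP wording and one additional imputation analysis. No new data are needed.

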The research activities involve a two-arm prospective RCT enrolling a sample of 600 AMSM with the aim of maintaining a randomized sample of approximately 500 online-recruited AMSM (13-18), assuming 15-20% attrition. After consent and completion of the online baseline survey, AMSM are randomized to either the control or experimental condition (Intervention, n=300; Control, n=300). Participants in the control arm will receive access to only the resource locator function of iReach, allowing them to search for local resources. Participants recruited nationally will receive a list of national resources. Participants in the experimental arm will receive access to all iReach functions, including life skills education, goal setting, local/national resource directory, a discussion forum related to life skills and goal setting, and the ability to link to a Peer Mentor through the VSee video-chat function. After consent and a baseline survey, AMSM are randomized to either the attention control or intervention condition. Self-completed study assessments are conducted online every three months across the intervention and attention-control follow-up time points, with a total follow-up period of 12 months for participants initially randomized into the intervention group, and 15 months for participants initially randomized into the control group. In months 12 to 15, we will make the intervention accessible to AMSM in the attention-control condition. The primary outcomes are cognitive (e.g., HIV prevention attitudes, norms, self-efficacy, behavioral intentions); behavioral outcomes are secondary (e.g., condom use, HIV testing, PrEP use). The proposed study design thus tests the impact of an e-delivered life skills intervention with an embedded video-chat peer motivational interviewing function on cognitive and behavioral HIV-related outcomes on a large (n=600) sample of AMSM.

The study is funded for approximately 5 years (Project Period: 07/28/2016 to 02/28/2021). Once consented, participants randomized into the intervention group will be active in the study for 12 months. Participants randomized into the control group will be active in the study for 15 months.

METHODS:

1. Study Instruments:

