Not applicable.

5. Statistical Analysis:

Descriptive statistics of the psychosocial and demographic characteristics of the participants will be described for all and by intervention group. These will be compared between treatment groups using t-tests or Wilcoxon rank sum tests for continuous variables and chi-square tests for categorical variables. In addition, we will use the general framework of generalized linear mixed models (GLMM) to test for intervention effects over time. Note that some of our outcomes are binary, some count and some continuous traits and thus need to be treated differently. The general form of the GLMM will be $\mu_{ij} = \beta_0 + \beta_1 \text{cov} + \beta_2 \text{Time} + \beta_3 \text{InterventionGroup} + \beta_4 \text{Group} \times \text{Time}$, where μ_{ij} is the mean response corresponding to subject i at Time j (baseline and 4 follow-ups) with the appropriate link function (identity for continuous outcome, logit for binary outcome and natural log for count outcomes); Group = 1 if the i -th subject is in the intervention group and 0 if the i -th subject is in the attention-control group. The interaction coefficients β_4 (Group \times Time) are of interest here, measuring the difference in the rate of change in outcomes across the two treatment groups over time. The subject-specific random intercepts β_0i are assumed to be normally distributed with a common variance and they account for within-person correlation. We will also explore if we need a subject specific random-slope corresponding to visit in the above model. Maximum likelihood estimation will be used for fixed effect parameters. Models will be compared according to information criterion like AIC, BIC. For some binary outcomes like HIV testing, we will perform an aggregate analysis after collapsing across the repeated measures using simple logistic regression comparing whether the probability of having tested at least once over the entire FU period is different across treatment groups, after adjusting for baseline values. To ensure robustness, we will also apply an exchangeable working correlation structure to its corresponding generalized estimating equation (GEE) model. We will also conduct exploratory regression analyses to examine differences based on social determinants of interest: age group, race/ethnicity, and rurality. These regressions will be run with group assignment and the social determinant variables of interest in the models, controlling for region. Interactions between group assignment and these social determinants will be tested to explore potential group-specific moderators of treatment effect. Given our focus on disparities, we also intend to examine mean differences across sub-groups of interest (e.g., race/ethnicity, developmental age group, urban vs. suburban vs. rural). For example, assuming we used a fixed effects ANOVA model with main effects and interactions by race and intervention condition, we would be able to detect any interaction effect size f of .18 in cross-sectional analyses at 80% power using a two-sided significance level of .05. Similar interaction effect sizes are obtained for developmental age (i.e., early (ages 13-14) vs. middle (ages 15-16) vs. late (ages 17-18) adolescence) and rurality (i.e., urban vs. sub-urban vs. rural). Secondary Analyses: Building on our GLMM framework employed for Aim 2, we will examine whether there are intervention effects in the socioecological factors (e.g., LGBT discrimination; HIV stigma) and life skills components (e.g., personal competence; identity development) associated with our outcomes. The regressions will be run with group assignment only in the model, as well as controlling for participants socio-demographic characteristics, psychological distress, and intervention-related process data (e.g., frequency of use, acceptability). In addition, we will test whether these relationships vary as a function of AMSMs varying engagement with the intervention (e.g., dose analysis; intervention acceptability, frequency of site log-ins; time spent on sites and modules; number and length of VSee sessions used). Interactions between group assignment and these characteristics will be tested to explore potential moderators of treatment effect. Recognizing that social determinants operate beyond the individual-level, we will use HLM to test how regional characteristics influence AMSMs outcomes. HLM allows us to take into account that participants are nested within regions, and examine whether regional characteristics are associated with individual-level outcomes. We will link individual and regional level data using participants residential address at enrollment. Some participants may be residentially unstable and/or would not want to give their exact location. We will estimate a two-level model to account for individual and regional variation.

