Eligible individuals must (1) have been assigned a male sex at birth and identify as male at the time of enrollment into the study (cis-gender male), (2) be between the ages of 13 and 18 years (inclusive), (3) speak and read English, (4) report same-sex attractions and/or behaviors, (5) have access to the Internet, (6) live in one of the zip codes at least partially contained in the 109 counties included in the four regions selected for this trial, and (7) self-report as HIV-negative at time of enrollment.

Randomization and Blinding

Participants are randomized on a 1:1 basis using a stratified randomization by race and region. AMSM will be randomized to one of two arms, with 300 randomized to each arm (complete data on 250 AMSM per arm, allowing for attrition of 50 AMSM per arm).

Study Assessments

The proposed domains mirror the theoretical framework informing our intervention. We include a summary of the primary and secondary outcomes, key intervention mechanisms of change, and potential covariates. Assessments will not take more than 25 minutes to complete. We have taken several steps to ensure that the assessments are brief and developmentally appropriate. First, AMSM will not answer all listed constructs at every assessment. Identity-related constructs, for example, will be measured at 6-month intervals, whereas other constructs (e.g., comfort discussing sexuality) will be assessed at each follow-up. Second, consistent with best practices that we have used in prior HIV studies with pediatric and adolescent populations^{142,256}, we will use gate-keeping questions to decide whether participants should receive other probes within a domain. For example, a participant who has yet to become sexually active would receive cognitive assessments focused on HIV risk and awareness (e.g., attitudes, norms), but would not receive questions regarding behavioral intentions to engage in HIV prevention in next 3 months (e.g., HIV testing, PrEP) or questions regarding sexual risk behaviors (e.g., sexual behavior, HIV testing, PrEP use). Similarly, at each assessment, AMSM with no lifetime substance use will not be asked about additional substance use questions. Among sexually active participants, gatekeeping also provides opportunities to regulate how detailed the assessments will be.

Domain	Assessment time					
	Baseline	Month 3	Month 6	Month 9	Month 12	Month 15
Primary outcomes						
HIV knowledge	X		X		X	X
Condom use/communication efficacy	X		X		X	X

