HIV/STI testing	X		X		X	X
Outcomes required for analysis						
Demographics	X		X		X	X
Patient provider communication around sexual orientation		X		X		
Stigma		X		X		
Resilience		X		X		
Psychological needs	X		X		X	X
Future life goals		X		X		
Secondary outcomes						
Internalized homonegativity	X		X		X	X
PrEP use and willingness [X		X		X	X
Sex behaviors	X		X		X	X
Substance abuse	X		X		X	X
Depression	X		X		X	X
Anxiety	X		X		X	X
Self-Esteem	X		X		X	X
Covariates						
Peer influence		X		X		
Family support		X		X		
Discrimination		X		X		
Online behaviors		X		X		
Societal reaction to sexual orientation		X		X		
Ethnicity beliefs		X		X		
Relationship history	X		X		X	X
Intervention acceptability		X				

Sample Size

Our expected sample size for analyses across both conditions is N=600 (Intervention, n=300; Control, n=300), assuming a 15-20% loss to follow-up. We estimated the minimum detectable effect sizes at 80% power, for comparisons of the two groups for the continuous primary cognitive (e.g., behavioral intentions, attitudes, norms, self-efficacy) outcomes, as well as the difference in the proportion of AMSM who report increased behavioral in the outcomes (e.g., condom use, HIV testing) to engage in HIV prevention services and behaviors in our treatment arm vs. our attention-control arm. For mean differences, our sample size calculations are based on a two-sample t-test assuming equal variance using a two-sided significance of 0.05. At 80% power, we can detect a between-arm difference of $d=0.22$ at the final follow-up. For repeated measure analyses, assuming a within-person correlation of 0.25, we would be able to detect a difference of 0.08. A less favorable within-person correlation of 0.75 allows us to detect an effect size of 0.11. For proportions, our sample size calculations are based on a two-sample test of proportions using a two-sided significance of 0.05. To have 80% power to compare active treatment to the control group, we require at least 500 participants to find a 12.5% difference between treatment and control in cross-sectional analyses. Assuming within-person correlation of 0.25, we can detect an 8.8% difference. A less favorable within-person correlation of 0.75 allows us to detect an 11.3% difference.

Timing of Analyses

Final analysis will be conducted once the desired sample size is recruited has reached and completed the last study assessment.

Analysis Populations

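### For the continuous primary outcomes, testing Group × Time with a free baseline Group term is valid but gives up precision; how much depends on the waves and variances

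*SAP*

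**What the plan says.** - **Model.** SAP, Efficacy Analyses (and Protocol, 5. Statistical Analysis) specifies a generalized linear mixed model with covariates, Time, Group and Group × Time. The response times are "baseline and 4 follow-ups", so baseline is an outcome occasion. The coefficients of interest are those of Group × Time, "measuring the difference in the rate of change in outcomes across the two treatment groups over time in the primary and secondary outcomes". Neither document says whether Time is linear or categorical, or names a 12-month contrast.
- **Covariance.** The Protocol says the subject-specific intercepts "are assumed to be normally distributed with a common variance and they account for within-person correlation". It adds that a random slope will be explored; the SAP does not mention one.
- **Baseline.** Protocol, Methods 3, places the baseline survey before assignment. Baseline adjustment appears only in the collapsed logistic analysis of outcomes such as HIV testing, "after adjusting for baseline values".
- **Waves.** The assessment table (SAP, Study Assessments) marks HIV knowledge and "Condom use/communication efficacy" at baseline and months 6, 12 and 15. Month 15 is not comparative; Protocol, Study Design: "In months 12 to 15, we will make the intervention accessible to AMSM in the attention-control condition".
- **Sizing.** SAP, Sample Size gives a "between-arm difference of $d=0.22$ at the final follow-up", and separate repeated-measures figures at within-person correlations of 0.25 and 0.75.
- **Missing data.** The SAP will use "likelihood-based methods that include partial information in cases that drop out prematurely".

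**The concern.** Randomisation after the baseline survey means that the arms share the same expected baseline mean. A model with its own Group term estimates that difference anyway, and Group × Time is then measured relative to a noisy baseline contrast. When the within-person correlation is low, subtracting a noisy baseline adds more variance than it removes, so the test can be less precise than one that ignores baseline. What is at stake is power for the continuous primary outcomes, using data that the trial collects in any case. Because Time coding and the tested contrast are also open, the documents do not fix which quantity the efficacy claim would rest on.

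**Working it through.** **Inputs from the plan:** waves 0, 6 and 12 months (assessment table); random intercept, hence equal correlation ρ between waves; ρ = 0.25 and 0.75; two-sided 0.05; 80% power; d = 0.22; 250 per arm with complete data. **Assumed:** ρ = 0.50, equal variance at each wave (SD 1), and the dropout patterns below.

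**The plan's own figure.** The detectable d for a two-sample test is (1.960 + 0.842) × √(2/n). This gives 0.251 at n = 250 per arm and 0.229 at n = 300; d = 0.22 would need 325 per arm. So 0.22 is not reproduced two-sided; a one-sided 0.05 test with 250 per arm gives 0.222. The ratios below do not depend on this figure. The power values simply take d = 0.22 as the target.

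**Variances.** Write the variance of the 12-month between-arm contrast as (2/n) × v.
- Group × Time with a free Group term: v = 2(1 − ρ), for linear or categorical Time with three equally spaced complete waves.
- Common baseline mean, categorical Time, 12-month contrast: v = 1 − ρ².
- 12 months only, ignoring baseline: v = 1.
- Ratio of the first two: 2(1 − ρ)/(1 − ρ²) = 2/(1 + ρ).

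| | ρ = 0.25 | ρ = 0.50 | ρ = 0.75 |
|---|---|---|---|
| v, free Group term | 1.50 | 1.00 | 0.50 |
| v, common baseline | 0.9375 | 0.75 | 0.4375 |
| Ratio of N | 1.60 | 1.33 | 1.14 |
| Detectable d, 250 per arm | 0.307 vs 0.243 | 0.251 vs 0.217 | 0.177 vs 0.166 |
| Power at d = 0.22, 250 per arm | 52% vs 72% | 69% vs 81% | 94% vs 96% |
| Total N for d = 0.22 | 974 vs 610 | 650 vs 488 | 326 vs 284 |

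Ignoring baseline gives 69% power at d = 0.22 with 250 per arm, whatever ρ is. The planned test falls below that when 2(1 − ρ) > 1, that is, when ρ < 0.50.

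**Dropout.** With an assumed 300/275/250 per arm at 0/6/12 months and partial cases kept, the ratio is 1.50/1.28/1.12. With 300/270/240 it is 1.48/1.27/1.11.

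**Unequal variances.** If the 12-month variance is k times the baseline variance, the ratio is (1 + k − 2ρ√k)/(k(1 − ρ²)). For an assumed k = 1.5:
- ρ = 0.25: (2.5 − 0.612)/1.406 = 1.34
- ρ = 0.75: (2.5 − 1.837)/0.656 = 1.01

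For k = 0.8 the range is 1.80 to 1.31.

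**Five waves, as in the model text.** With linear Time over 0 to 1, the sum of squares about the mean is 0.625, so v = (1 − ρ)/0.625 = 1.20/0.80/0.40. Against the common-baseline 12-month contrast the ratio is 1.28/1.07/0.91, if the effect really is linear. With categorical Time it stays 1.60/1.33/1.14.

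**Same Time coding, only the Group term dropped.** For linear Time with m waves, v = (1 − ρ)/[Σt² − ρ(Σt)²/(1 + (m − 1)ρ)]. At ρ = 0.25:
- Three waves: 0.75/(1.25 − 0.375) = 0.857, ratio 1.50/0.857 = 1.75
- Five waves: 0.75/(1.875 − 0.781) = 0.686, ratio 1.20/0.686 = 1.75

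Across ρ = 0.25/0.50/0.75 the ratios are 1.75/1.375/1.15 (three waves) and 1.75/1.33/1.125 (five waves).

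**The case against.** The strongest case is that the planned test is a legitimate test of change, for endpoints defined as change, and that the size of the loss is conditional. Several parts of this stand.

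- **Wave count.** The range 1.60 to 1.14 takes the assessment table as correct. On the model text's five waves, with a linear slope and a linear effect, the planned test at ρ = 0.75 is more precise than a 12-month contrast (0.91). The mismatch therefore has to be settled before the loss can be quoted as one number.
- **Variance.** Equal variances are assumed, and the Protocol leaves a random slope open. The figures for k show that the range moves both ways.
- **Mixed sources.** The correlations come from the repeated-measures sizing statements, and d = 0.22 from the final-follow-up comparison. The trial is not sized on the latter alone.
- **High correlation.** At ρ = 0.75 the power loss is about two percentage points.

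The argument that the endpoint is change does not rescue the free Group term. With a common expected baseline, the 12-month difference between arms equals the difference in change from baseline to month 12.

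Three stronger readings are tempting, but the documents do not support them. First, a reader might infer bias or an invalid test; randomisation rules that out for the free Group term. Second, a reader might infer that a categorical 12-month contrast is always better; the 0.91 shows otherwise. Third, constructs marked only at months 3 and 9, such as stigma and future life goals, might seem bound to a Group × Time test that misses an effect already present at month 3. The Protocol's secondary-analysis text builds on the same model, but then says that these regressions are run with group assignment alone, and also with covariates. That most naturally makes Group the tested term, so this needs clarification only.

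**Conclusion.** The concern holds as a loss of precision in a valid test, for continuous outcomes with a baseline measure. With three complete waves, a random intercept and equal variances, the planned test needs 1.60 to 1.14 times the sample size of a common-baseline 12-month contrast over the plan's own correlations, or about 1.5 to 1.1 with the assumed dropout. At ρ = 0.25 it is less precise than ignoring baseline; at 0.75 the loss is small. Under the random-intercept, equal-variance model with complete data, removing the free Group term gains precision under either wave count when Time coding is held fixed. Moving from a slope to a 12-month contrast is a separate choice, and a trade-off if there are five waves, ρ is high and the effect is linear.

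**What to change.** 1. For continuous outcomes with a baseline measure, constrain the arms to a common baseline mean in the efficacy model, or adjust for the baseline value.
2. State whether Time is linear or categorical, and name the tested contrast. Categorical Time with the 12-month contrast matches the final-follow-up sizing, subject to the trade-off noted above.
3. Reconcile the wave count in the model text of both documents with the waves marked for each outcome in the assessment table.
4. For constructs marked only at months 3 and 9, add a sentence confirming that the Group term is tested.

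The cost is SAP wording and a changed model statement, with no new data. Item 1 is limited to continuous outcomes, because with logit or log links baseline adjustment changes the conditional estimand. It does not address items that are skipped for participants who are not yet sexually active.
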